7.2.1 DISCONTINUATION CRITERIA

Regardless of the inciting agent, the following warrant treatment discontinuation:

- Treatment related adverse reactions that are life-threatening.
- Treatment related diarrhea or colitis, grade 4; also administer high-dose systemic corticosteroids.
- Infusion-related reaction, grade 4.
- Treatment related immune-related Pneumonitis, Grade 2 or higher; also administer high-dose systemic corticosteroids.

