4 STUDY DESIGN

4.1 OVERVIEW OF STUDY DESIGN

This is an open label, Phase II trial of acalabrutinib and high frequency low dose subcutaneous rituximab in previously untreated CLL patients requiring therapy. Subjects will be recruited from the James P. Wilmot Cancer Center, University of Rochester in Rochester, New York. Patients seen in the inpatient or outpatient setting with histologically confirmed untreated CLL will be evaluated for this study.

Patients will be treated with the following combination:

Rituximab: day 1 = 50 mg IV, then 50 mg SQ 2 x weekly for 6 cycles. Note that in the event of a first dose infusion reaction, subsequent doses may be given IV if felt necessary by the treating investigator.

Acalabrutinib: 100 mg po BID starting on day 8 of cycle 1. First dose prior to rituximab on day 8.

- Response assessments will be performed prior to the completion of cycle 12. Patients who have attained a radiographic complete response will undergo a BM biopsy to confirm CR. Patients in CR will also have MRD testing performed on peripheral blood and marrow. Patients in CR and undetectable for MRD, will stop therapy and be followed until disease progression.
- Patients not in a MRD negative CR, will continue acalabrutinib.
- Repeat response assessments will be performed at 24 cycles of therapy for those continuing on acalabrutinib. Patients in CR and undetectable for MRD, will stop therapy and be followed until disease progression, unacceptable toxicity or physician/patient discretion.

All cycles will be 28 days.

Patients will be followed until the occurrence of definitive disease progression and may discontinue therapy early for unacceptable toxicity or withdrawal from the study due to investigator decision or other reasons.

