7.2 STUDY DRUG MODIFICATIONS

- The actions should be taken for any Grade 4 toxicity or unmanageable Grade 3 toxicity. In addition, the actions in Table 7.2.1 should be taken when modification of acalabrutinib dose is recommended for specific treatment-related adverse events as listed in Table 7.2.2.
- If the dose of acalabrutinib is reduced, at the Investigator's discretion, the dose of acalabrutinib may be re-escalated after 2 cycles of a dose reduction in the absence of a recurrence of the toxicity that led to the reduction. Dose changes must be recorded in the study documentation.
- Dose modifications are for adverse events attributed to study treatment. Dose modifications are not required for adverse events unrelated to study treatment.
- Guidance for dose modifications in the event of drug interactions is provided in Table 6.2.1

TABLE 7.2.1: DOSE MODIFICATION ACTIONS FOR ACALABRUTINIB

Event Occurrence	Action
1 st -2 nd	May restart at original dose level (100 mg BID)
3 rd	Restart at 100 mg daily
4 th	Discontinue acalabrutinib

TABLE 7.2.2: STUDY DRUG MODIFICATIONS

	Rituximab	Acalabrutinib
NCI-CTCAE Grade		
Neutropenia		
Grade 3 neutropenia	Maintain current dose	Maintain current dose

	Rituximab	Acalabrutinib
Grade 4 neutropenia lasting >7 days or occurrence of neutropenic fever or infection	Delay rituximab until Grade ≤ 3 and/or neutropenic fever or infection is resolved; thereafter, resume at full dose. If delay is > 4 weeks, discontinue rituximab.	Hold acalabrutinib until recovery of Grade ≤ 3 or baseline. Follow dose modification actions in TABLE 7.2.1.
Thrombocytopenia		
Grade 3 thrombocytopenia	Maintain current dose	Maintain current dose
Grade 4 thrombocytopenia	Delay rituximab until Grade ≤ 3; thereafter resume at full dose. If delay is > 4 weeks, discontinue rituximab.	Hold acalabrutinib until recovery of Grade ≤ 3 or baseline. Follow dose modification actions in TABLE 7.2.1.
Diarrhea (non-infectious)		
Grade 1: increase of <4 stools per day over baseline	n/a	Provide antidiarrheal (eg, loperamide) and maintain current acalabrutinib dose level and schedule.
Grade 2: increase of 4-6 stools per day over baseline	n/a	Provide antidiarrheal (eg, loperamide). Withhold acalabrutinib until Grade ≤ 1. Resume acalabrutinib at current dose level. If rechallenge results in recurrence, may resume at initial or lower dose level at investigator discretion (if applicable). Consider addition of anti-inflammatory (eg, sulfasalazine, budesonide).

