Grade 3: increase of >7 stools per day over baseline	n/a	Provide antidiarrheal (eg, loperamide). Withhold acalabrutinib until Grade ≤ 1. Resume at lower dose level (if applicable). Consider addition of anti-inflammatory (eg, sulfasalazine, budesonide).
Grade 4: life-threatening	n/a	Provide antidiarrheal (eg, loperamide). Withhold acalabrutinib until Grade ≤ 1. May resume at lower dose level (if applicable) or discontinue acalabrutinib at investigator discretion. Consider addition of anti-inflammatory (eg, sulfasalazine, budesonide).
Immune related pneumonitis		
Grade 1	Withhold rituximab until resolved. Resume at full dose or if delay >4 weeks, discontinue rituximab	Maintain current dose. Consider pneumocystis prophylaxis
Grade ≥2	Discontinue rituximab, consider systemic corticosteroids and pneumocystis treatment.	Discontinue acalabrutinib, consider systemic corticosteroids and pneumocystis treatment.
Rash or injection site reaction		
Grade 1	Maintain current dose	Maintain current dose
Grade 2	Withhold rituximab until Grade ≤ 1. Resume at full dose or if delay >4 weeks, discontinue rituximab.	Maintain current dose

	Rituximab	Acalabrutinib
Grade 3 or 4	Withhold rituximab until Grade \leq 1. Resume at full dose or if delay >4 weeks, discontinue rituximab.	Withhold acalabrutinib until Grade \leq 1, consider systemic corticosteroids. Follow dose modification actions in TABLE 7.2.1.
All Other Non-Hematological Adverse Events		
Grade 3	Withhold rituximab until Grade \leq 1. Resume at full dose or if delay >4 weeks, discontinue rituximab.	Hold acalabrutinib until recovery of Grade \leq 1 or baseline. Follow dose modification actions in TABLE 7.2.1.
Grade 4	Discontinue rituximab.	Hold acalabrutinib until recovery of Grade \leq 1 or baseline. Follow dose modification actions in TABLE 7.2.1.

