7.2.2 CRITERIA FOR ONGOING TREATMENT

Continue treatment as per protocol provided that patient has:

- No intolerable toxicities related to study drug.
 - Treatment may be delayed to recover from toxicity.
- No clinical or radiographic evidence of disease progression.
- Not withdrawn from the study for other reasons.

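### For treatment-related, non-infectious Grade 4 diarrhea, Section 7.2.1 calls for treatment discontinuation while Table 7.2.2 lets acalabrutinib resume, and nothing says which rule governs

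*Combined protocol and SAP*

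**What the plan says.** Section 7.2.1 (Discontinuation Criteria) opens with "Regardless of the inciting agent, the following warrant treatment discontinuation". One of its four bullets is "Treatment related diarrhea or colitis, grade 4; also administer high-dose systemic corticosteroids".

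Table 7.2.2, in its block for non-infectious diarrhea, labels the top row "Grade 4: life-threatening". For acalabrutinib the row calls for an antidiarrheal and a hold until Grade 1 or less. It then continues: "May resume at lower dose level (if applicable) or discontinue acalabrutinib at investigator discretion". The rituximab cell is marked not applicable.

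Section 7.2 sets the scope of the tables: "Dose modifications are for adverse events attributed to study treatment". Its first bullet also says that the Table 7.2.1 actions are to be taken when an acalabrutinib modification is recommended for treatment-related events listed in Table 7.2.2. Table 7.2.1 allows restart at 100 mg BID after the first and second occurrence, restart at 100 mg daily after the third, and discontinuation at the fourth.

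**The concern.** The two passages give different answers about acalabrutinib for the same event. Section 7.2.1 provides for stopping and leaves no route back to treatment. The table row expressly allows a return. The question is whether to re-expose a patient after an event that the table itself labels life-threatening, so the protocol should answer it in only one way.

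As written, one patient could be taken off treatment and the next re-challenged, and neither decision could clearly be called a deviation. The monitoring committee, which under Section 10.5 receives reports of withdrawals and dose adjustments, would have no single standard to judge them by. The summaries of discontinuations (Section 9.2) and dose modifications (Section 9.4) would partly reflect which passage the treating investigator happened to follow.

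**Working it through.** The plan has no figure to reproduce on this point. The check is a comparison of texts, followed by a rough sense of scale.

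**1. Is it the same event?** Section 7.2.1 covers treatment-related Grade 4 diarrhea. The table row covers non-infectious Grade 4 diarrhea, and Section 7.2 confines dose modifications to events attributed to study treatment. Infectious diarrhea falls outside the row, and unrelated diarrhea falls outside Section 7.2.1. The overlap is treatment-related, non-infectious, Grade 4 diarrhea, and the point is limited to it.

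**2. Are the actions different?**

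| Source | Acalabrutinib | Rituximab |
|---|---|---|
| Section 7.2.1 | Treatment discontinuation warranted, whichever agent is the cause | Not addressed separately; treatment is not defined as one drug or both |
| Table 7.2.2, Grade 4 diarrhea row | Hold to Grade 1 or less, then resume at a lower level or discontinue, at discretion | Not applicable |
| Table 7.2.1, if Section 7.2 brings it in | First and second restart may be at the original dose; third at 100 mg daily; discontinue at the fourth | Not covered |

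An investigator who discontinues acalabrutinib satisfies the first two rows. One who resumes it satisfies only the table row. If Table 7.2.1 also applies, its original-dose restart differs from the lower dose level in the row.

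**3. Does any passage set precedence?**
- Section 4.3 lists severe toxicity as a reason to stop, without a grade or a cross-reference.
- Section 7.1 lets a patient who stops one drug continue the other. It does not say which rule decides that acalabrutinib stops.
- Section 7.2.2 makes continuation conditional on "No intolerable toxicities related to study drug", which names neither the event nor the governing rule.

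None of these resolves the conflict.

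**4. When does the rituximab side matter?** Rituximab is given as 50 mg IV on day 1, "then 50 mg SQ 2 x weekly for 6 cycles". The nominal window is 6 × 28 = 168 days. Section 7.1 allows delays of up to four weeks, so the actual window can run longer.

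**5. How many patients?** The documents give no Grade 4 diarrhea rate. Section 1.4 lists the most frequent Grade 3 or higher events for acalabrutinib monotherapy (lowest listed 3.1%) and for acalabrutinib with obinutuzumab (lowest listed 6.7%). Diarrhea is on neither list. Assume that an unlisted event is no more frequent than the lowest listed one, and that those rates carry over to this trial. The expected number with Grade 3 or higher diarrhea among 40 patients is then no more than:
- 40 × 0.031 = 1.24
- 40 × 0.067 = 2.68

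These are expected counts, not ceilings. With a binomial count of 40 patients, two or more would occur with probability 0.35 at 3.1%, and three or more with probability 0.51 at 6.7%. The 95th percentiles are 3 and 5 patients. Grade 4 events are a subset of these.

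**The case against.** The best defense is that to warrant can mean to justify rather than to require, so that Section 7.2.1 says when stopping is reasonable and the table supplies the detail. The protocol's own usage weighs against this. Pneumonitis of Grade 2 or higher is in the same Section 7.2.1 list, and Table 7.2.2 makes it an outright discontinuation of both drugs. List and table agree there and part company for Grade 4 diarrhea. If the permissive reading was meant, no passage says so.

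It is also fair to say that the practical reach is small. There is one center, so the divergence is between investigators or patients, not sites. Few patients are likely to be involved, and discontinuing acalabrutinib satisfies both passages. All of that stands and limits the consequences, but it does not remove the contradiction.

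A reader might infer more than the documents support:
- **Unlimited re-challenge.** The row states no limit on resumptions, but the first bullet of Section 7.2 can be read to bring in Table 7.2.1, which ends in discontinuation at the fourth occurrence.
- **A second, independent conflict.** The row label seems to trigger the other Section 7.2.1 bullet, "Treatment related adverse reactions that are life-threatening". That bullet does not say which sense of the term it uses, and Section 10.2 defines life-threatening, for seriousness, as immediate risk of death. The point therefore rests on the diarrhea bullet alone.
- **A conflict over corticosteroids.** Section 7.2.1 calls for high-dose systemic corticosteroids, while the row suggests considering an anti-inflammatory. Both can be followed in the same patient.

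**Conclusion.** The contradiction is confirmed for one event: treatment-related, non-infectious Grade 4 diarrhea. Section 7.2.1 and Table 7.2.2 lead to different actions on acalabrutinib, Table 7.2.1 may add a third, and no passage ranks them. Whether rituximab must also stop is unclear during the rituximab cycles.

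This conclusion needs no numerical assumption. The view that few patients would be affected does rest on assumptions, namely those in step 5 of the working.

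The point should be fixed because it is a safety rule with two answers, not because of its statistical effect. A reader might infer that the primary result is compromised, and the documents do not support that. Under Section 9.6 the CR rate is computed on all treated patients, with unassessed patients counted as non-responders, so the denominator is the same whichever rule is followed. Nothing in the documents shows how either rule would change an individual patient's response.

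**What to change.** Amend the protocol so that treatment-related, non-infectious Grade 4 diarrhea has one action:
- Reconcile Section 7.2.1, the Grade 4 diarrhea row of Table 7.2.2, and the reference to Table 7.2.1 in the first bullet of Section 7.2.
- State which passage governs if they differ.
- State whether treatment in Section 7.2.1 means the causative drug, acalabrutinib alone, or both drugs, and make the rituximab cell of the row agree.

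The choice of rule belongs to the sponsor's clinical team, and none is proposed here. The cost is amendment wording and a notice to the treating investigators. No procedures, visits or patients are added.

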7.2.2 CRITERIA FOR ONGOING TREATMENT

Continue treatment as per protocol provided that patient has:

- No intolerable toxicities related to study drug.
 - Treatment may be delayed to recover from toxicity.
- No clinical or radiographic evidence of disease progression.
- Not withdrawn from the study for other reasons.

7.3 CONCOMITANT MEDICATIONS

Concomitant use of acalabrutinib with strong CYP3A inhibitors (e.g., ketoconazole, conivaptan, clarithromycin, indinavir, itraconazole, lopinavir, ritonavir, telaprevir, posaconazole and voriconazole) is not allowed.

Avoid concomitant use of moderate CYP3A inhibitors (e.g., erythromycin, ciprofloxacin, diltiazem, dronedarone, fluconazole, verapamil) with acalabrutinib if feasible. If a moderate CYP3A inhibitor must be used, reduce the acalabrutinib dose to 100 mg once daily.

Avoid concomitant use of strong CYP3A inducers (e.g., carbamazepine, phenytoin, rifampin, St. John's wort) if feasible. If a strong CYP3A inducer must be used, increase the acalabrutinib dose to 200 mg twice daily.

7.4 ORDERING RITUXIMAB AND ACALABRUTINIB

Acalabrutinib will be supplied at no charge by Acerta/Astra Zeneca.

Upon receipt of treatment supplies, the Pharmacist or the appropriate person of the site should update the accountability forms. If any abnormality on the bottles is observed, the Pharmacist or the appropriate person must document that on the acknowledgement of receipt and contact that Sponsor and/or Sponsor designee.

Rituximab will be ordered by the trial site via commercial channels.

8 MEASUREMENT OF EFFECT

During the study period, all patients will be evaluated for response by history, examination, CT and/or MRI and bone marrow assessment. After cycle 24, all efficacy assessments should be per investigator discretion or standard of care. All efficacy assessments have a +/- 7 day window. The determination of response and progression will be based on the IWCLL criteria for CLL and SLL patients. [37]

CT scan is the preferred method of tumor assessment but MRI may be used at the investigator's discretion. The same method of assessment and the same technique should be used to characterize each identified and reported lesion at baseline and throughout the study.

Patients will remain on study treatment until achievement of MRD negative CR at 12 or 24 months, the occurrence of definitive disease progression, unacceptable toxicity, or withdrawal from the study due to investigator decision or other reasons. Patients who discontinue from study treatment (either for toxicity or physician choice) and have not progressed will continue to be followed for disease progression.

8.1 METHOD OF ASSESSMENT

In addition to clinical examination, imaging-based evaluation will be used in this study in all patients enrolled. CT scan is the preferred method for radiographic tumor assessment. MRI scanning may be used at the investigator's discretion in patients for whom this may be a preferred alternative to CT scanning. Contrast-enhanced scanning is preferred, but iodine-containing or gadolinium contrast material may be omitted in patients for whom use of a contrast agent would be medically contraindicated. Chest x-ray, ultrasound, endoscopy, laparoscopy, radionuclide scans, or tumor markers will not be considered for response assessment.

For radiographic evaluations, the same method of assessment and the same technique (e.g., scan type, scanner, patient position, dose of contrast, injection/scan interval) should be used to characterize each identified and reported lesion at baseline and during study treatment and follow-up. However, if a patient is imaged without contrast at baseline, subsequent assessments should be performed with contrast, unless the patient cannot tolerate the contrast.

8.2 IDENTIFICATION AND MEASUREMENT OF TUMOR LESIONS AND ORGANOMEGLALY

8.2.1 TARGET LESIONS

For patients with measurable adenopathy/disease at baseline, up to 6 lymph nodes should be selected as target lesions that will be used to quantitate the status of the disease during study treatment. Ideally, the target lesions should be located in disparate regions of the body. Only peripheral nodes need be selected as target lesions. However, it is optimal if mediastinal and retroperitoneal areas of disease are assessed whenever these sites are involved.

Target lesions will be measured and recorded at baseline and as per the study assessment schedule. The cross-sectional dimensions (the largest cross-sectional diameter, i.e., the LD x LPD) will be recorded (in cm) for each target lesion. The product of the perpendicular diameters (PPD) (in cm²) for each target

lesion and the sum of the products (SPD) (in cm^2) for all target lesions will be calculated and recorded. The baseline SPD will be used as references by which objective tumor response will be characterized during treatment. The nadir LD of individual lesions and the nadir SPD will be used as references by which CLL progression will be characterized. All LD and LPD diameters will be reported in centimeters and all PPDs and SPDs will be reported in centimeters squared.

A nodal mass may be selected as a nodal target lesion if it is both abnormal and measurable at baseline. A lymph node lesion is considered abnormal if it has a single diameter that is $> 1.5 \text{ cm}$ and is considered measurable if it has 2 perpendicular diameters that can be accurately measured in cross section with the LD being $\geq 1.0 \text{ cm}$ and the LPD also being $\geq 1.0 \text{ cm}$.

At follow-up time points, the LDs for individual lesions and the SPD of all nodal target lesions will be considered. Because nodal target lesions that have one or both diameters $> 0 \text{ cm}$ and $< 1.0 \text{ cm}$ cannot be reliably measured, a default value of 1.0 cm will be assigned for each diameter that meets these criteria and the resulting PPD will be used in SPD calculations. Based on this convention, a CR may be achieved even if an SPD value is $> 0 \text{ cm}^2$ (i.e., if all lymph nodes measure $< 1.0 \text{ cm}^2$).

A new node that measures $> 1.5 \text{ cm}$ in the LD and $> 1.0 \text{ cm}$ in the LPD will be considered progressive disease.

In cases in which a large lymph node mass has split into multiple components, all subcomponents regardless of size will be used in calculating the SPD. Progression of the lesion will be based on the SPD of sub-components. Lesion sub-components will have the true PPDs calculated. Similarly, lesion sub-components that are visible but neither abnormal nor measurable will have the default PPD of 1.0 cm^2 ($1.0 \text{ cm} \times 1.0 \text{ cm}$) used in calculating the SPD.

If lesions merge, a boundary between the lesions will be established so the LD of each individual lesion can continue to be measured. If the lesions have merged in a way that they can no longer be separated by this boundary, the newly merged lesion will be measured bi-dimensionally.

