5 STUDY ASSESSMENTS AND TREATMENT SCHEDULE

Table 5.1 below lists all of the required assessments that should be performed at each study visit.

TABLE 5.1: STUDY ASSESSMENTS AND TREATMENT SCHEDULE

Cycle = 28 days	Screening	Cycle 1 ¹				Cycle 2-6 ²	Cycle 7-12 ²	Cycles 12-24 ²	Follow up ³
	D-28 to -1	D1	D3,4 or 5	D8	D15	D1	D1	q3 mo	
Informed consent	X								
Medical history	X								
ECOG Performance Status	X								
Physical Examination	X	X		X		X	X	X	
Vital signs	X	X	X	X		X	X	X	
Hematology ¹⁴	X	X	X	X	X	X	X	X	
Chemistry ¹⁵	X	X ¹⁶				X	X	X	
LDH, Uric acid	X	X ¹⁶							
B2mcg	X								
Pregnancy Test	X ⁸								
Hep B/C serology, quant IgG	X								
FISH	X ⁵								
IGHV, TP53, NOTCH1, SF3B1	X ⁵								
CT imaging (neck, chest, abdomen, pelvis)	X ⁶					X ⁶	X ⁶		
BM aspirate & biopsy						X ⁹	X ⁹		
Flow cytometry for MRD						X ¹⁰	X ¹⁰		
Correlative Labs ⁴	X	X	X	X	X	X	X	X	
Rituximab 50 mg* twice weekly	X*	X	X	X	X				
Acalabrutinib 100 mg BID			X ¹³	X	X	X	X ¹²	X ¹²	
Response Assessment						X	X		
Adverse Event Assessment		X	X	X	X	X	X	X	X ¹¹
Concomitant Medications		X	X	X	X	X	X	X	

*1st dose of rituximab will be administered intravenously, subsequently doses will be administered subcutaneously

¹ Treatment Administration +/- 1 day window. Physical Exam, Vital Signs, Hematology and Chem visit days have - 1 day window

² Treatment Administration +/- 3 day window. Physical Exam, Vital Signs, Hematology and Chem visit days have a - 3 day window

³ Following completion of cycle 24 or upon discontinuation of therapy in the absence of disease progression, patients will be evaluated as per institutional standards (typically every 3-4 months). Physical exam data, vital signs, laboratory values and patient diaries will no longer be collected. Patients continuing on acalabrutinib will continue with adverse event assessments at each evaluation and be followed for progression and survival events.

⁴ See section 12

⁵ FISH for del17p, del11q, del13q, trisomy 12 will be performed on peripheral blood or marrow within 6 months of C1D1. IGHV, TP53, NOTCH1, SF3B1 mutation analysis to be performed at screening (if feasible) unless previously tested.

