8.2.3 NON-TARGET LESIONS

Any other measurable and abnormal nodal lesions not selected for quantitation as target lesions may be considered non-target lesions. In addition, non-measurable evidence of CLL such as nodal lesions with both diameters $< 1.0 \text{ cm}$, extra-nodal lesions, bone lesions, leptomeningeal disease, ascites, pleural or pericardial effusions, lymphangitis of the skin or lung, abdominal masses that are not confirmed and followed by imaging techniques, cystic lesions, previously irradiated lesions, and lesions with artifacts may be considered as non-target disease.

The presence or absence of non-target disease should be recorded at baseline and at the stipulated intervals during treatment. If present at baseline, up to 6 non-target lesions should be recorded. The non-target disease at baseline will be used as a general reference to further characterize regression or

progression of CLL during assessments of the objective tumor response during treatment. Measurements are not required and these lesions should be followed as “present” or “absent”.

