8.5 PARTIAL RESPONSE

To satisfy criteria for a PR, all of the following criteria must be met:

- No evidence of new disease
- Change in disease status meeting ≥ 2 of the following criteria, with 2 exceptions in which only 1 criterion is needed: 1) only lymphadenopathy is present at baseline; 2) only lymphadenopathy

Acalabrutinib + low dose SQ Rituximab

Dated: 06OCT2022

Page 38 of 59

and lymphocytosis are present at baseline. In these 2 cases, only lymphadenopathy must improve to the extent specified below:

- In a patient with baseline lymphocytosis (ALC $\geq 4 \times 10^9/L$), a decrease in peripheral blood ALC by $\geq 50\%$ from baseline or a decrease to $< 4 \times 10^9/L$
- A decrease by $\geq 50\%$ from the baseline in the SPD of the target nodal lesions
- In a patient with enlargement of the liver or spleen at baseline, a decrease by $\geq 50\%$ from baseline
- A decrease by $\geq 50\%$ from baseline in the CLL marrow infiltrate or in B-lymphoid nodules
- No target, splenic, liver, or non-target disease with worsening that meets the criteria for definitive PD
- Peripheral blood counts meeting 1 of the following criteria:
 - ANC $> 1.5 \times 10^9/L$ or $> 50\%$ increase over baseline without need for exogenous growth factors (e.g., G-CSF)
 - Platelet count $> 100 \times 10^9/L$ or $\geq 50\%$ increase over baseline without need for exogenous growth factors
 - Hemoglobin $> 110 \text{ g/L}$ (11.0 g/dL) or $\geq 50\%$ increase over baseline without red blood cell transfusions or need for exogenous growth factors (e.g., erythropoietin)

PR criteria met but without recovery of lymphocytosis = PR-L

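### Section 8.2.1 lets peripheral nodes alone serve as target lesions, so in patients whose baseline disease is nodal (with or without lymphocytosis) partial response can be scored while a dominant internal mass is unchanged

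*Combined protocol and SAP*

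**What the plan says.** Section 8.2.1 sets the number of targets as "up to 6 lymph nodes should be selected as target lesions". On location it says "Ideally, the target lesions should be located in disparate regions of the body", then "Only peripheral nodes need be selected as target lesions", then "However, it is optimal if mediastinal and retroperitoneal areas of disease are assessed whenever these sites are involved". The first and last of these three sentences are advice. The middle one says what is sufficient. Nothing tells the reader to choose the largest nodes.

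Under 8.2.3, abnormal measurable nodes that are not selected may be classed as non-target. For these, "Measurements are not required and these lesions should be followed as" present or absent.

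Under 8.5, the only nodal shrinkage criterion for PR is a decrease of at least 50% "from the baseline in the SPD of the target nodal lesions". In general two of four disease criteria must be met (lymphocyte count, target SPD, liver or spleen, marrow), "with 2 exceptions in which only 1 criterion is needed": baseline disease that is lymphadenopathy only, or lymphadenopathy plus lymphocytosis. In those two cases the nodal criterion decides. Non-target disease blocks PR only if it worsens enough to be definitive progression.

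Section 9.6 defines ORR as PR or CR. Section 2.2 lists duration of response as a secondary objective.

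**The concern.** A PR is meant to say that the disease as a whole has shrunk. Here the SPD can be built entirely from small peripheral nodes in a patient whose main disease is in the abdomen or mediastinum. The internal mass is then recorded only as present, which is the same entry whether it has halved or not changed.

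This fits poorly with the rest of the protocol. Nodes of 10 cm or more are one of the indications for treatment in 3.1, Table 5.1 schedules CT from neck to pelvis, and 8.3 ranks imaging above physical examination. The information is collected but need not enter the PR call. Two readers could also choose different targets in the same patient, both comply with 8.2.1, and reach different response categories.

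PR and ORR are at stake. Progression is affected to a lesser degree: 8.7 has a limb based on a 50% rise from nadir in the long diameter of an individual node, but no measurement is required for an unselected mass, so there may be no nadir to compare with.

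**Working it through.** **The plan's own figures.** The only design figures concern the CR rate. The exact 95% interval for 8/40 is 9.05% to 35.65%, width 26.6 points, and the maximum width at n = 40 is 32.4 points (at 20/40). Both agree with section 9.1. Neither depends on how targets are chosen.

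**The rule for the nodal criterion.** Let B and F be the baseline and follow-up SPD of the peripheral nodes, and M the product of diameters of an internal mass that does not change.

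- Peripheral targets only: fall = (B − F) / B.
- Mass also a target: fall = (B − F) / (B + M).
- PR needs a fall of at least 50%.

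**Illustration (sizes are assumptions; the documents give none).** Two axillary nodes go from 3 × 2 cm to 1.4 × 1.0 cm, and a 12 × 10 cm mesenteric mass is unchanged.

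- B = 2 × 3 × 2 = 12 cm²; F = 2 × 1.4 × 1.0 = 2.8 cm²; M = 12 × 10 = 120 cm².
- Without the mass: (12 − 2.8) / 12 = 76.7% fall. Nodal criterion met.
- With the mass: (132 − 122.8) / 132 = 7.0% fall. Nodal criterion not met.

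The result does not need an extreme mass. The call reverses whenever (B − F) / (B + M) < 0.5, that is, M > B − 2F. Here that is 12 − 5.6 = 6.4 cm².

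**Range of assumed sizes.** Six peripheral targets, compared with five of them plus the unchanged mass, which keeps the six-lesion cap:

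| Peripheral node, baseline → follow-up (cm) | Fall, six peripheral targets | Fall with 6 × 5 mass | Fall with 10 × 8 mass | Fall with 10 × 10 mass |
|---|---|---|---|---|
| 2 × 2 → 1 × 1 | 75% | 30% | 15% | 12.5% |
| 3 × 2 → 1.5 × 1.5 | 62.5% | 31.2% | 17% | 14.4% |
| 3 × 2.5 → 1.5 × 1.5 | 70% | 38.9% | 22.3% | 19.1% |

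In all nine combinations the criterion is met without the mass and missed with it.

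**From criterion to response.** If baseline disease is nodal, with or without lymphocytosis, and the remaining 8.5 conditions hold (no new disease, one blood count criterion, no PD-level worsening), the first result is a PR and the second is not. In other patients SPD is one of four criteria of which two are needed. Lymphocyte count plus spleen, for example, can give PR with no nodal shrinkage whichever nodes are targets.

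**CR.** Section 8.4 requires all nodal non-target disease to return to normal, so an unchanged mass blocks CR whether or not it is a target.

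**Scale for ORR.** One misclassified patient among 40 treated is 1/40 = 2.5 points. The number of such patients would require four shares: patients whose largest node is internal, those for whom SPD alone decides PR, those for whom only peripheral targets are picked, and those with discordant shrinkage. The documents give none of them.

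**The case against.** The best defence is that the neighbouring sentences steer readers away from the worst case: targets should ideally be spread across regions, and internal sites should be assessed when involved. That is fair as a guide to likely practice. It does not bind, and it sits beside a sentence saying peripheral nodes suffice.

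It is also true that little rests on PR. The primary endpoint is CR, ORR appears in 9.6 but not among the listed objectives, and 4.3 stops treatment for MRD-negative CR or CRi, not for PR. This limits the importance of the point but does not remove the gap.

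A reader might infer more than the documents support:

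- *That PR always turns on target SPD.* It does so only in the two exceptions in 8.5.
- *That growth of an internal mass is left wholly to judgement.* Section 8.7 also has the 50% long-diameter limb, which is not restricted to targets. The weakness is the missing nadir measurement.
- *That an unblinded investigator picks the lesions.* The documents do not say who selects them, and 8.3 has an IRC categorise response. An IRC applying 8.2.1 would still be working under the same permissive rule.
- *That duration of response starts from a false response.* The plan does not define its starting point. It is affected only if counted from PR.
- *That ORR is inflated by a stated number of points.* No such figure can be derived.

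**Conclusion.** The point holds as a minor defect in a measurement rule. Sections 8.2.1, 8.2.3 and 8.5 together permit a PR, and hence a responder in the ORR, while the dominant internal mass is unchanged. The clear case is the patient whose baseline disease is lymphadenopathy with or without lymphocytosis. The lesion sizes above are assumed and show only that the nodal call can reverse, not how often it would. The size of the effect on ORR is unknown, and the primary CR rate is unaffected. Because PR in other patients can be reached without nodal shrinkage, better target selection closes only part of the gap.

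**What to change.** Replace the sentence on peripheral nodes, and the advisory sentences around it, with:

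> Select up to six measurable abnormal nodes on the baseline CT/MRI. The largest node or nodal mass must be included, whatever its site; then add the largest measurable node from each other involved region, including mediastinal and retroperitoneal/mesenteric regions, up to six in total.

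This gives a clear order of priority, keeps the six-lesion cap, and supplies the baseline and nadir measurements that 8.7 needs for such a mass. For patients already enrolled, apply the same rule to their existing baseline scans, and re-measure later scans to match, so that one rule underlies the ORR.

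The cost is a protocol amendment with IRB review under 11.1, some re-measurement of existing scans, and possibly a slightly lower ORR. No additional scan or visit is needed.
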